8.1.2 Imputation of Partial Dates

Imputed dates will not be used to derive study day, duration (eg, duration of adverse events), or elapsed time variables. In addition, imputed dates are not used for deriving the last contact date for overall survival. Imputed dates will be displayed in listings and identified as imputed.

Partial date imputation will follow Analysis Data Model (ADaM) conventions. The ADaM approach is to populate the numeric date variables with the imputed date and add a flag variable to the dataset that indicates the level of imputation.

The flag variable can contain the values: blank, 'D', 'M', 'Y'.

blank: indicates that no imputation was done

D = 'Day': indicates that the day portion of the date is imputed

M = 'Month': indicates that the month and day portions of the date are imputed

Y = 'Year': indicates that the entire date (year, month, and day) is imputed

Algorithms for imputing partial dates for AE and concomitant medications are below.

Imputations in the adverse events dataset are used for slotting events to the appropriate study time periods and for sorting in data listings. They will not be used to calculate duration of AEs. If an AE start or end date is missing, then the duration of the AE will be set to missing.

Adverse Events

Impose start and end dates for use to derive the reference variables for adverse event start relative to treatment; include any imputed dates in analysis datasets with an identifier as imputed. The reference variables will be used to differentiate as Before-therapy, On-Therapy and Follow-up for AEs (see [Section 8.3.2](#)).

Date	Missing Element	Rule
Start Date	day, month, and year	Do not impute completely missing AE start dates, AE will be assumed as treatment emergent
	day and month	
• If the onset year is after the year of the first dose of study drug, then the AE is treatment-emergent.• If the onset year is the same as the year of the first dose of study drug and the end date is not before the first dose of study drug, then the AE is treatment-emergent.• If the onset year is the same as the year of the first dose of study drug and the end date is before the first dose of study drug, then the AE is not treatment-emergent.• If the onset year is before the year of the first dose of study drug, then the AE is not treatment-emergent.

Date	Missing Element	Rule
	day only	
• If the start yyyy-mm is after the yyyy-mm of first dose of study drug, then the AE is treatment-emergent.• If the start yyyy-mm is the same as the yyyy-mm of the first dose of study drug and the end date is not before the first dose of study drug, then the AE is treatment-emergent.• If the start yyyy-mm is the same as the yyyy-mm of the first dose of study drug and the end date is before the first dose of study drug, then the AE is not treatment-emergent.• If the onset yyyy-mm is before the yyyy-mm of the first dose of study drug, then the AE is not treatment-emergent.
End Date	any date element	No imputation for completely or partially missing AE end dates; as applicable, report the AE as ongoing and the AE duration as missing.

Concomitant Medication

Impute start and end dates for use to derive the reference variables for concomitant medication start and end relative to treatment; include any imputed dates in analysis datasets with an identifier as imputed. The reference variables will be used to differentiate before, during and after treatment for the concomitant medication.

Date	Missing Element	Rule
Start Date	day, month, and year	Do not impute completely missing concomitant medication start dates.
	day and month	
• If the onset year is after the year of the first dose of study drug, then the CM is concomitant.• If the onset year is the same as the year of the first dose of study drug and the end date is not before the first dose of study drug, then the CM is concomitant.• If the onset year is the same as the year of the first dose of study drug and the end date is before the first dose of study drug, then the CM is prior.• If the onset year is before the year of the first dose of study drug, then the CM is prior.

Date	Missing Element	Rule
	day only	
• If the start yyyy-mm is after the yyyy-mm of first dose of study drug, then the CM is concomitant.• If the start yyyy-mm is the same as the yyyy-mm of the first dose of study drug and the end date is not before the first dose of study drug, then the CM is concomitant.• If the start yyyy-mm is the same as the yyyy-mm of the first dose of study drug and the end date is before the first dose of study drug, then the CM is prior.• If the onset yyyy-mm is before the yyyy-mm of the first dose of study drug, then the CM is prior.

Date of Birth

Imputation for birth date is only needed if age is missing on eCRF and needs to be recalculated. An incomplete birth date will be imputed as follows:

If only the day is missing – the missing day will be imputed as 15th of the month.

If day and month is missing – missing day and month will be imputed by 1st of July.

A completely missing birth date will not be imputed.

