8.3.3 Study Time Periods for Prior and Concomitant Medications

Prior medications are those ending in the before-therapy period.

Concomitant medications include those that start during the before-therapy period and continue into the on-therapy and Follow-up periods as well as those that start during the on-therapy and Follow-up time periods. Therapies that start during the before-therapy period and have a missing end date will be assumed to continue into the on-therapy period and, therefore, will also be considered concomitant medications.

9 Study Population

Only data of subjects who provided informed consent (informed consent date available in the database) will be included in the statistical analysis.

Unless otherwise stated, all tables and listings in this section will be based on the mITT and / or Safety Analysis Set, and all summaries and data listings will use treatment descriptors as specified in [Section 7.2](#).

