9.4 Prior and Concomitant Medications

Prior and Concomitant medications will be coded using CSL Behring Drug coding dictionary (WHO-DDE Enhanced 2016MAR, B2 Format), summarized, and listed. The summary of prior and concomitant medications will show the number and percentage of subjects taking prior/concomitant medications. Anatomical Therapeutic Chemical (ATC) classification Level 1 (Body System) information will be included in the dataset created but will not appear on the listing or summary. ATC Level 4 and preferred term of prior/concomitant medications will be used for summaries and listings. If the ATC Level 4 coding is not available for a preferred term, the next available lower level ATC code will be used. The summary will be provided by treatment group for RWS Analysis Set and overall for the RiS Analysis Set.

Concomitant medication start and end dates relative to treatment start and end dates are used to select data to include in summaries as follows:

- Summary of Concomitant Medications: This summary will contain medications with start dates relative to treatment assigned to ('BEFORE', 'DURING') and end dates relative to treatment assigned to ('DURING', 'AFTER').

- Summary of Concomitant Medications with On-Therapy Onset: This summary will contain medications with start dates relative to treatment assigned ('DURING') and end dates relative to treatment assigned to ('DURING', 'AFTER').

In the summary of concomitant medications, each subject is counted once within each unique term. For example, if a subject takes Amoxycillin on two separate occasions, the subject is counted only once under the ingredient "Amoxycillin".

Concomitant medications will be summarized separately for medications with onset date within the on-therapy period and for medications with onset date within the before-therapy period.

Note: In order to be considered a concomitant medication, the concomitant medication must have been taken at some point during the on-therapy window.

Concomitant medications will be summarized for the RWS Analysis Set and overall and for RiS Analysis Set.

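### For partial start dates, SAP 8.1.2 labels an earlier-started medication prior whatever its end date, against SAP 8.3.3, SAP 9.4 and protocol 8.4

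*SAP*

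**What the plan says.** SAP 8.1.2 limits its rules to incomplete dates: "Algorithms for imputing partial dates for AE and concomitant medications are below". For medications it has one block for starts with day and month missing and one for starts with only the day missing. The same-year and same-month bullets look at the end date, for example "the end date is not before the first dose of study drug, then the CM is concomitant". The last bullet of each block does not:

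- Day and month missing: "If the onset year is before the year of the first dose of study drug, then the CM is prior".
- Day only missing: "If the onset yyyy-mm is before the yyyy-mm of the first dose of study drug, then the CM is prior".

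SAP 8.3.3 gives the general definitions:

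- A drug is prior by its end, not its start: "Prior medications are those ending in the before-therapy period".
- A drug begun earlier and still taken falls in the other class: "Concomitant medications include those that start during the before-therapy period and continue into the on-therapy and Follow-up periods".
- An unknown end is resolved the same way: "Therapies that start during the before-therapy period and have a missing end date will be assumed to continue into the on-therapy period". Such drugs therefore count as concomitant.

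SAP 9.4 builds the concomitant summary from medications whose start is BEFORE or DURING treatment and whose end is DURING or AFTER. It adds that the drug must have been taken at some time in the on-therapy window. It also plans a separate summary of concomitant medications with onset before therapy. Protocol 8.4 likewise regards a therapy already being given at consent, and continued alongside investigational product, as concomitant.

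**The concern.** Whether a drug is prior or concomitant depends on whether it was still being taken once treatment began. A rule that looks only at the start cannot answer that for a drug begun earlier. The medication bullets follow the pattern of the adverse-event bullets in the same section, with concomitant in place of treatment-emergent and prior in place of not treatment-emergent. For adverse events onset decides, so leaving out the end date does no harm there. For medications it gives the wrong class whenever the drug is ongoing.

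At stake is the description of background therapy. Protocol 7.2 permits maintenance immunosuppression and steroids, and in transplant recipients these may well have begun long before enrollment. If such drugs carry partial start dates and the 8.1.2 label is used, the concomitant-medication summary understates what subjects were taking alongside study drug.

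**Working it through.** The plan states no figure to reproduce. The check sets the two SAP rules side by side in every possible case.

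**Inputs.** The 8.1.2 label comes from the medication bullets. The 8.3.3 label is prior if the drug ended before the first dose and concomitant otherwise, with a missing end date taken as continuing. End dates are taken as either known or wholly missing.

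**Cases.** There are two levels of start precision (day missing; day and month missing). The known part of the start is before, the same as, or after that of the first dose. The end is before the first dose, after it, or ongoing/missing. A start after the first-dose period with an end before the first dose is impossible. Each precision level therefore has 3 + 3 + 2 = 8 cells, and 2 × 8 = 16 in all. The results are the same at both levels:

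| Start period vs first dose | End | 8.1.2 | 8.3.3 | Agree? |
|---|---|---|---|---|
| Before | Before first dose | prior | prior | yes |
| Before | After first dose | prior | concomitant | **no** |
| Before | Ongoing/missing | prior | concomitant | **no** |
| Same | Before first dose | prior | prior | yes |
| Same | After first dose | concomitant | concomitant | yes |
| Same | Ongoing/missing | concomitant | concomitant | yes |
| After | After first dose | concomitant | concomitant | yes |
| After | Ongoing/missing | concomitant | concomitant | yes |

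Conflicts: 2 per level × 2 levels = 4 of 16. The rules agree in the other 12. Complete start dates are outside 8.1.2 and are classed by 8.3.3 and 9.4 without difficulty.

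**With an end-date condition on the before rows.** The two conflicting rows become concomitant, and conflicts fall from 4 of 16 to 0 of 16.

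**Illustration (dates invented).** The first dose is in 2019 and the drug is ongoing. A start recorded as 2019 gives concomitant under 8.1.2. A start of 15 March 2018 is complete, so 8.3.3 gives concomitant. A start recorded only as 2018 gives prior under 8.1.2. The last two may be the same drug with the same exposure; only the completeness of the date differs.

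**Precedence.** SAP 8.3.1 refers incomplete dates to 8.1.2 when events and medications are assigned to periods. No section says which rule prevails when 8.1.2 and 8.3.3 differ.

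**The case against.** The strongest reply is that the table in SAP 9.4 does not select on a prior or concomitant label. It selects on start and end relative to treatment, and 8.1.2 introduces its medication rules as a way to derive exactly those reference variables. On that reading a partial start in an earlier year simply gives a start of BEFORE. Under 8.3.3 a missing end date is taken as continuing, and BEFORE with an end of DURING or AFTER is admitted to the table. Nothing is lost.

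This stands as a possible reading, and it is why the effect must be stated conditionally. It does not remove the contradiction. The 8.1.2 bullets end in a class, not in an imputed date or a BEFORE flag. A programmer who applies that class departs from 8.3.3; one who applies 8.3.3 departs from 8.1.2.

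It is also fair to say that 9.4 has prior as well as concomitant medications summarized and listed, so even on the worst reading no record disappears from the report.

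A reader might infer more than the documents support:

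- *That every earlier-started medication is misclassed.* Only those with a partial start date and continued use are exposed.
- *That maintenance immunosuppressants drop out of the concomitant table.* This follows only if the 8.1.2 label overrides 8.3.3 and 9.4, which the SAP does not say.
- *That long-running drugs are the likeliest to have partial dates.* This is plausible, but the documents contain nothing on it.
- *That each affected subject moves an arm by 14 to 17 percentage points.* SAP section 3 gives 13 randomized subjects; 1/7 = 14% and 1/6 = 17% require a 7:6 split that is not reported. SAP 9.4 also counts a subject once per term, so a second qualifying record of the same drug would leave the percentage unchanged.

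**Conclusion.** The inconsistency is real and narrow. For partial start dates before the first-dose year or month, SAP 8.1.2 gives prior where SAP 8.3.3, SAP 9.4 and protocol 8.4 make a continuing drug concomitant. The two SAP rules conflict in 4 of 16 partial-date cells. Any understatement of background therapy depends on two things the documents leave open: that such records exist, and that the 8.1.2 label is the one applied. The number of affected records is not given and could be zero.

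The affected output is a descriptive medication summary in a study that was terminated early and has no formal hypothesis testing. No endpoint is affected. Severity: minor.

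**What to change.** Replace the last bullet in both medication blocks of SAP 8.1.2 (day and month missing; day only missing) with:

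*If the onset year (yyyy-mm) is before that of the first dose, the CM is prior if its end date is before the first dose; otherwise, including ongoing or missing end date, it is concomitant.*

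This brings 8.1.2 into line with 8.3.3 and 9.4. The cost is one sentence, used in two places, and one programming condition. If the programs already follow 8.3.3, record that in the clinical study report, where SAP section 7 says deviations from the SAP will be identified.

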8.2 Derived Variables

The following sections provide a general description of the derived variables for data analyses.

8.2.1 Reference Dates

Reference dates are used to assign study periods relative to treatment.

There are three reference dates:

- Because age is an eligibility requirement, the reference date for age is the date of screening.
- The safety reference date is the date of first C1-INH dosing in Treatment Period 1 and will be used to calculate study day for safety measures.
- The reference date for efficacy endpoints is the date of first intake of randomized study treatment in Treatment Period 2 and will be used to calculate study day for efficacy measures.

8.2.2 Study Day for Safety Measures

If the date of interest occurs on or after the safety reference date, then the safety study day will be calculated as (date of interest - safety reference date) + 1. If the date of interest occurs before the safety reference date, then the safety study day will be calculated as (date of interest – safety reference date). There is no safety study day 0.

8.2.3 Study Day for Efficacy

The study day for efficacy will be calculated in the same manner as the study day for safety measures but will consider the reference date for efficacy. There is no efficacy Study Day 0.

Timings for safety events and interventions

Safety events and interventions will be classified as follows:

Before-treatment: Date is strictly prior to the first administration of open-label C1-INH.

Treatment-emergent or On-Treatment: Date is between the first administration of open-label C1-INH and 30 days after the investigational product stop date.

Post-treatment: Date is strictly more than 30 days after the investigational product stop date.

8.2.4 Durations

Durations (eg, the duration of an adverse event) and elapsed time will be calculated in days using the SAS DATDIF function.

When reporting durations which are calculated in months, divide the number of days by 30.4375; to report in weeks divide the number of days by 7; to report in years divide the number of days by 365.25. These algorithms for time to event return decimal numbers, and ignore the actual numbers of days in the months or years between start date and stop date. The "year" used in these algorithms is 365.25 days long, and the "month" is one twelfth of that year.

8.2.5 Baseline Definition

Baseline for non-laboratory and laboratory data (except creatinine for eGFR) is defined as the most recent, non-missing value prior to or on the first study treatment dose date/time in Treatment Period 1 (for non-laboratory it is referred to eCRF data and for laboratory data it is referred to local laboratory data).

For subjects who did not receive study treatment during the study, a baseline value will not be calculated. The most recent, non-missing value prior to or on the study treatment dose date / time is based on scheduled assessments only.

Baseline eGFR has been defined as follows in original protocol and amendments:

- For subjects randomized prior to Protocol Amendment 1, dated November 28, 2017, the nadir (minimum) of the eGFR values from screening and Day 1 will be used as the baseline.
- For subjects randomized after Protocol Amendment 1 the mean of the screening and Day 1 values will be used as the baseline.

For the purpose of analysis, baseline eGFR is defined as the mean of the screening and Day 1 values.

Note that a set of vital signs or laboratory values may have different dates for baseline values.

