- ^f A pregnancy test will be conducted for women of childbearing potential, only. Serum pregnancy test will be conducted at Screening and Week 12. Urine or serum pregnancy tests will be conducted at all other timepoints. If the screening pregnancy test is conducted within 24 hours of Day 1, then an additional pregnancy test is not needed on Day 1.
- ^g A blood sample will be retained for potential future serology assessments.
- ^h Creatinine will be measured by the central laboratory ([CL]) and as a part of the serum biochemistry panel by the local laboratory. The complete list of assessments included as a part of the biochemistry panel is presented in [Table 13](#).
- ⁱ Donor-specific antibodies will be measured in both the central and local laboratories. Central laboratory results will be used for analyses. Local laboratory results will be used by the investigator to make treatment decisions, including the initiation of plasmapheresis. Donor-specific antibodies should be tested in the local laboratory within between 24 and 72 hours after completing plasmapheresis.
- ^j Sequential PK **CCI** [REDACTED] sampling from a subset of subjects will occur on the Day 10 and Week 11 Visits. See [Table 6](#) for additional details.
- ^k Intravenous C1-INH will be administered at a dose of 60 IU/kg at the study site. Intravenous C1-INH should be administered with a minimum of 48 hours between each dose.
- ^l Subcutaneous C1-INH will be administered at a dose of 60 IU/kg every 3 or 4 days (ie, twice weekly) at the study site, at home by a medical professional, or at home by the subject under the supervision of a medical professional. The first dose of subcutaneous C1-INH should be administered between 24 and 48 hours after the last dose of intravenous C1-INH.
- ^m Intravenous immunoglobulin will be administered at a dose of 2 grams/kg. Administration of the dose will begin at the visit. The dose must be administered over a minimum period of at least 2 days, and may be administered over a period of up to 5 days (see [Section 5.4.1](#) for details).
- ⁿ **CCI** [REDACTED]
- ^o Responders will be randomized to treatment with blinded investigational product during Treatment Period 2. The definition of response is provided in [Section 10.3.1](#). Non-responders will enter a 45-month Non-responder Follow-up Period.

CSL Behring LLC

CSL842_3001

C1-esterase Inhibitor, Human (500 IU/mL)

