8.1.3.5 Donor-specific Antibody (DSA)

Donor-specific antibody identification and specificity will be performed using a tiered approach. DSA to HLA Class I and Class II antigens will be identified by the Luminex solid-phase single-bead antigen immunoassay. If any DSA is \geq 5000 MFI on a neat serum sample, then dilution testing of 1:16 should be performed to determine if the DSA drops to below 2000 MFI or remains strong (\geq 5000 MFI). Additional titers may be tested at the discretion of the investigator. Local DSA results will not be recorded in the eCRFs.

Decisions regarding the conduct of plasmapheresis will be based on local laboratory analysis of DSA, as outlined in [Section 5.4.2](#). Samples will also be sent for central laboratory testing. Central laboratory results will be used for analyses.

Additional details regarding the assessment of DSA will be presented in the laboratory manual.

8.1.3.6 **CCI [REDACTED]**

CCI [REDACTED]

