8.1.1 Imputation of Non-Date Missing Data

Non-date Clinical Data

All available data will be analyzed using suitable statistical methods. For analysis of percent responders, all subjects in the appropriate analysis set (ITT Analysis Set or mITT Analysis Set) will be included in the denominator when calculating the percentages; any subject who drops out of the study at any time after randomization will be defined for the purpose of analysis as a non-responder.

Subjects with the designation of treatment relationship for adverse events (AEs) and serious adverse events (SAEs) missing will have the worst case assumed to impute the relationship: if relationship to study treatment is missing it will be assumed to be “Yes”.

In summaries of absolute values and change from baseline, subjects with missing baseline values will not be included in baseline rows or in the change from baseline summary statistics.

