11.7.2 Hematology

All hematology parameters for this study will be summarized by scheduled visit using descriptive statistics. All unscheduled visits will be excluded from these by-visit summaries.

Open-label hematology data and that for the entire study will be summarized for the RiS Analysis Set.

Double-blind hematology data will be summarized for the RWS Analysis Set by treatment.

Hematology parameter to be summarized: Hemoglobin, hematocrit, red blood cell indices: mean corpuscular hemoglobin, mean corpuscular hemoglobin concentration, mean corpuscular volume, blood cell counts: basophils, eosinophils, erythrocytes, leukocytes, lymphocytes, monocytes, neutrophils, neutrophil band forms, platelets, and reticulocytes.

DSA: will be included as efficacy endpoint and will therefore be summarized for efficacy.

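### SAP 8.2.5 takes the DSA baseline from local laboratory data, but the protocol analyses central DSA and keeps local DSA out of the eCRFs

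*SAP*

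**What the plan says.** The baseline rule in SAP 8.2.5 covers everything but one analyte: "Baseline for non-laboratory and laboratory data (except creatinine for eGFR) is defined as the most recent, non-missing value" up to the first dose in Treatment Period 1. A parenthesis then names the sources. Non-laboratory data come from the eCRF, and "for laboratory data it is referred to local laboratory data". The rule uses scheduled assessments only.

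The protocol treats DSA differently. Table 1, footnote i: "Donor-specific antibodies will be measured in both the central and local laboratories. Central laboratory results will be used for analyses". Table 2, footnote f, and Sections 5.4.2 and 8.1.3.5 also reserve the central results for analysis. Local results serve the investigator's treatment decisions, and Section 8.1.3.5 states: "Local DSA results will not be recorded in the eCRFs".

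Two further SAP statements matter. On missing baselines, 8.1.1 says that "subjects with missing baseline values will not be included in baseline rows or in the change from baseline summary statistics". On the role of DSA, 11.7.2 says: "DSA: will be included as efficacy endpoint and will therefore be summarized for efficacy".

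**The concern.** Local sourcing suits serum chemistry and hematology. It does not suit DSA, which is a laboratory measurement, is not among the exceptions, and is analysed from another laboratory under the protocol. A programmer who follows the SAP as written would look for the DSA baseline in data that the protocol does not place in the eCRF. If local values were found by another route, the baseline and the follow-up values would come from different laboratories.

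At stake is the meaning of any DSA baseline row or change-from-baseline figure. A programmer who instead used central values on judgement would be departing from the SAP. Section 7 of the SAP requires such departures to be identified in the clinical study report.

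**Working it through.** The plan gives no figure on this point and no arithmetic on trial data applies. The check sets the texts side by side.

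| Question | SAP | Protocol |
|---|---|---|
| Which laboratory gives the DSA baseline? | Local, by the general rule in 8.2.5 | Central for analyses (Table 1 footnote i, Table 2 footnote f, 5.4.2, 8.1.3.5) |
| Is DSA an exception to that rule? | No; only creatinine for eGFR is named | Not applicable |
| Is local DSA captured? | Not stated for DSA | Not in the eCRFs (8.1.3.5) |
| Is a pre-dose central value planned? | Not stated for DSA | Day 1 draw before C1-INH and IVIg (8.5.3.1), with samples also sent for central testing (8.1.3.5) |
| Which visit is the laboratory baseline? | Last scheduled non-missing value up to first dose | Day 1 unless otherwise specified (10.3.1) |

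**Step 1, source.** Under 8.2.5 the DSA baseline is a local value. Under the protocol the analysed DSA value is central. The two texts cannot both be followed.

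**Step 2, first consequence.** If no local DSA value reaches the database, a literal application leaves no recorded DSA baseline. The 8.1.1 rule would then remove the affected subjects from any DSA baseline row and any change statistic.

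**Step 3, second consequence.** Suppose local values did reach the database. SAP 8.2.6 defines change as visit value minus baseline value. Write C for a central reading, L for a local one, subscript t for a post-baseline visit and 0 for baseline:

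C_t − L_0 = (C_t − C_0) + (C_0 − L_0)

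The first bracket is the change wanted. The second is the difference between the two laboratories' readings at baseline. The documents give no figure for that difference, so its size is unknown. Protocol 3.5 plans about 35 sites, so it need not be the same for all subjects.

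**Step 4, timing.** In the readable visit lists, Day 1 is the only scheduled pre-dose DSA draw. The SAP's date rule and the protocol's Day 1 rule therefore select the same visit. Only the source needs correcting.

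**Step 5, reach.** SAP 8.2.5 exempts creatinine for eGFR, so the primary endpoint does not pass through this rule.

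**The case against.** The strongest objection is that no affected output can be seen. No readable SAP section computes a DSA baseline or a DSA change, and DSA is not among the secondary endpoints in SAP Table 2. Nine numbered efficacy headings are blacked out (10.8, 10.9, 10.11, 10.13 to 10.17 and 10.19), and any of them could set its own DSA source. SAP Section 5 lists 11 endpoints that will only be listed by subject. Five of these are redacted, and if DSA is one of them there may be no baseline table at all. This stands, and it limits what can be said about impact. It does not remove the conflict, because the readable rule names its exception and omits DSA.

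A reader might infer that the DSA baseline is empty for all subjects. The documents do not say so. Section 8.1.3.5 speaks only of the eCRFs, while SAP 8.2.5 names local laboratory data separately from eCRF data. No readable text describes another transfer of local DSA, but none rules one out. Central Day 1 samples are also planned.

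A reader might also extend the point in three directions, and the documents support none of them:

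- **HLA-class subgroup (SAP 10.1.1).** It groups subjects by a category and does not invoke 8.2.5. The 8.1.1 exclusion concerns absolute values and change from baseline, not subgroup membership.
- **C1-esterase inhibitor activity and antigen.** These follow their own data flow and summary rules in SAP Section 12.
- **Immunoglobulin.** SAP 10.18 plans only a listing of trough IVIg concentrations at Weeks 12 and 32, which needs no baseline. No readable text names a central laboratory for this analyte or for C1-esterase inhibitor.

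**Conclusion.** The conflict is real for DSA and for no other analyte that the readable text supports. SAP 8.2.5 assigns a source that contradicts the protocol's repeated statement on central DSA, and the protocol keeps that source out of the eCRFs. The consequence is conditional: it affects only a DSA summary that uses baseline, and whether one exists cannot be confirmed.

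No percentage of subjects or size of bias can be attached. The conclusion assumes that 8.2.5 applies to DSA as written and that no redacted section overrides it. The stakes are small. The study was terminated with 13 subjects randomized (SAP Section 3), no formal testing is planned (SAP 4.2.1.3 and 7.3), and the primary endpoint's eGFR baseline is unaffected. This is a minor but definite correction.

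**What to change.** In SAP 8.2.5, restrict the local-laboratory source to serum chemistry and hematology. Add DSA to the exceptions alongside creatinine for eGFR, with the central laboratory Day 1 pre-dose value as its baseline. If a redacted section already sets the DSA source, a cross-reference from 8.2.5 to that section is enough.

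The cost is one clause. The sample is already scheduled and no new data are needed. If the SAP is not reissued, record the use of central DSA as a deviation in the clinical study report, as SAP Section 7 provides.
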